The main challenge to BUP discontinuation is that many patients experience significant and protracted discomfort, withdrawal--like symptoms with increase in craving as well as mood anxiety and sleep disruptions (Dunn et al., 2015). These symptoms emerge even as the dose is being gradually reduced. As a result, many will abandon the attempt at discontinuation and resume BUP maintenance. If the patient stops medication on their own, and cannot easily resume treatment, they may relapse to illicit opioids. Therefore, the question of how to discontinue treatment in patients who favorably responded to BUP is of high significance to the field as it may address several important questions with clinical relevance.

Specific Aims and Hypotheses

Specific Aims and Hypotheses

The primary outcome will be the percent of patients successfully transitioned off buprenorphine and abstinent from any opioids at the 25--week trial endpoint.

Secondary outcomes will include measures of opioid withdrawal, mood, anxiety and sleep problems, abstinence from other substances, time to relapse or dropout, and adverse effects.

Additionally we will examine in biofluid derived extracellular vesicle content for the existence of biomarkers related to naltrexone treatment.

We hypothesize that more patients will successfully discontinue buprenorphine in the group that received XR--NTX.

Description of Subject Population

Sample #1

Specify subject population

Adults ages 18-60 currently treated with buprenorphine for opioid use disorder

Number of completers required to accomplish study aims

50

Projected number of subjects who will be enrolled to obtain required number of completers

60

Age range of subject population

18-60

Gender, Racial and Ethnic Breakdown

Both males and females will be recruited. All eligible subjects are accepted; however, past experience with recruitment for other studies in this population suggests that that the sample will be 75% male, 60%

Caucasian, 30% Hispanic or Latino, and 10% Black or African-American.

Description of subject population

Adults ages 18-60 currently treated with buprenorphine for opioid use disorder

Recruitment Procedures

Describe settings where recruitment will occur

All potential participants will be evaluated at the BSU clinic at the New York State Psychiatric Institute.

How and by whom will subjects be approached and/or recruited?

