Evaluation of Depression and Anxiety symptoms: Participants who meet criteria for a Mood Disorder (MDD) of mild to moderate severity or an Anxiety Disorder will be followed closely during detoxification and subsequently. Mood and anxiety will be assessed both in therapy sessions and during MD visits. If a

patient demonstrates significant symptoms which persist following detoxification, we will offer the participant the option of beginning an antidepressant or an anti-anxiety treatment if deemed clinically warranted.

Managing controlled substances: Currently the study is run under the NYS Controlled Substance license # 0400081 held by the NYS OMH and the DEA Researcher Registration # PN0093461 held by the NYSPI Pharmacy Department. [name] has obtained his own NYS Controlled Substance license and a federal DEA research license. . The drug stock of controlled substances for each project will be ordered, maintained and prepared under the Institutional registration at the NYSPI Pharmacy (OMH/NYS Controlled Substance license # 0400081).

You can upload charts or diagrams if any

Criteria for Early Discontinuation

Criteria for Early Discontinuation

Drop out criteria during the study period include:

- 1) Development of serious psychiatric symptoms as indicated by the Clinical Global Impression (CGI) improvement score of 6 (much worse than baseline) or greater for 2 consecutive weeks or psychiatric or medical deterioration that cannot be managed safely in the context outpatient treatment offered at the study (in cases where the investigator determines that the participant needs immediate study discontinuation).
- 2) If the participant's continued opioid or other drug use places him/her at risk for self-destructive behavior or other harm as indicated by a CGI improvement score of 6 or more (much worse than baseline) for 2 consecutive weeks. In cases where the investigator determines that the participant needs immediate study discontinuation for continued opioid or other drug use, participants will be provided with referrals.
- 3) Development of serious medical condition(s) that may or may not be related to study participation as assessed by weekly visits with the psychiatrist, vital sign measurements, and weekly weight-ins.
- 4) If the participant becomes pregnant as assessed by monthly urine pregnancy testing
- 5) Ongoing non--adherence with recommended clinical visits, absence from study visits for 21 days.

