Systematic Assessment for Treatment and Emergent Events (SAFTEE): The SAFTEE as modified for Project COMBINE (Johnson et al., 2005) will be performed weekly, **and twice-monthly during study months 4-6** to identify any adverse symptoms. If participants report experiencing adverse symptoms since the previous visit, the research nurse will record the symptom as well as the date of onset, severity, and resolution (if applicable) and research psychiatrist will review it at least weekly and more frequently if symptoms are present.

Timeline Follow--Back (TLFB): The Timeline Followback method (Litten and Allen, 1992) will gather self-- reported opioid use data for each day during the month prior to study enrollment and each day during the study period. The TLFB confirmed by urine toxicology will be the primary outcome measure of psychoactive substance use and will be performed at **every study visit**.

Therapist Contact Log (TCL): The number and duration of treatment sessions will be documented by the therapist on a contact log.

End of Study Form (ESF): At study completion or the point of termination for patients who relapse or drop out, the research psychiatrist fills out an End of Study Form, which indicates whether or not a patient completed 25 weeks of treatment, the date of termination, the number of weeks of treatment completed from randomization to termination, and reasons for early termination, including documented relapse to opiates, resumption of buprenorphine maintenance, psychiatric worsening, medical worsening, or lost to follow--up.

Self--Report

Clinical Global Impression--Self (CGI--S): The CGI--Self is a two--item scale that asks the subject to rate his or her current level of symptoms and estimate changes from baseline (Guy, 1976). The CGI--S will serve as the primary self--reported measure of overall functioning.

Medical Outcomes Study--Sleep Scale (MOS--SS): The MOS--SM is a 12--item measure for characterizing the quality of sleep (Hays et al., 2005). Opioid withdrawal, both acute and protracted is characterized by insomnia and other sleep disturbances. The MOS--SM will be the primary outcome of sleep quality and length and will be collected at each visit.

Craving Scales-- Self: A visual analog scales is used for patients to rate the intensity of craving for opiates experienced since the previous visit ([name] et al., 2011).

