study visits vitals and a urine toxicology for opioids (morphine, oxycodone, buprenorphine, methadone, propoxyphene, and fentanyl), THC, cocaine, benzodiazepines, amphetamines, and metamphetamines will be collected. They will have scheduled meetings with a study psychiatrist weekly to inquire about medication effects and any changes in their medical/psychological condition following medication discontinuation.

The primary outcome will be the percent of patients successfully transitioned off buprenorphine and abstinent from any opioids at the 25-week trial endpoint. Secondary outcomes will include measures of opioid withdrawal, mood, anxiety and sleep problems, abstinence from other substances, time to relapse or dropout, and adverse effects. We hypothesize that more patients will successfully discontinue buprenorphine in the group that received XR-NTX.

This proposed exploratory trial will be able to inform the design of future research and clinical work. A positive signal that transition from maintenance buprenorphine to XR-NTX is feasible and prevents relapse would encourage a larger trial to replicate and perhaps extend to multiple community based treatment settings. A feasible, well-tolerated, and effective method of helping patients wishing to discontinue treatment with BUP has the potential to expand the population of opioid-dependent individuals benefitting from treatment.

A2. Primary and Secondary Outcome Measures

Primary Outcome: percent of patients successfully transitioned off buprenorphine and abstinent from any opioids at the 25-week trial endpoint.

Secondary Outcomes: 1) Measures of weekly opiate withdrawal (SOWS), mood (Ham-D, BDI), anxiety (HAM-A, STAI), and sleep (MOS-SS) (continuous, longitudinal); 2) Time to relapse (survival outcome); 3) Continuing abstinence at 12 and 25 weeks (dichotomous); 4) Dichotomous weekly summary measure of use (derived by combining urine and self-report, as measured by TLFB) reflecting whether each patient had urine-confirmed opiate-free weeks over the course of treatment and urine-confirmed abstinence from all drugs (dichotomous, longitudinal); 5) Adverse events (SAFTEE) (dichotomous).

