Study Aim #2: To determine whether treatment with XR-NTX reduces severity of protracted withdrawal seen following BUP discontinuation.

Significance testing and preliminary analysis:

All tests for main effects will be performed at two-tailed significance $\alpha=5\%$. We will examine all variables for outliers, the distributions of all continuous variables will be checked for normality and if needed transformations will be used before applying parametric techniques. The distribution of demographic variables and other covariate measures at baseline in the treatment arms will be examined (means, standard deviations, proportions and 95% confidence intervals). The analysis will be adjusted by three preselected covariates (primary opioid type, length of BUP maintenance, and average dose).

Primary Analyses

Subjects treated with XR-NTX will have significantly higher rates of successful transition off BUP at the end of study compared to subjects tapered off BUP. The effect of treatment on the primary outcome will be examined using logistic regression adjusted for specified covariates (primary opioid type, length of BUP maintenance, and average dose), and described using the estimated coefficients of the treatment term in the model, the corresponding odds ratios, and 95% confidence intervals.

Secondary Analyses

Longitudinal dichotomous and continuous outcomes will be modeled with generalized linear mixed effects models using appropriate link function (logit for dichotomous outcomes) with treatment, time, treatment by time interaction, and applicable baseline outcome measure as predictors. Time to relapse will be analyzed using survival analyses and Kaplan-Meier estimators. Dichotomous outcomes will be analyzed similarly to primary hypothesis with logistic regressions. The within subject correlation will be modeled using autoregressive AR(1) structure and random effects of subject. Significant time by treatment interaction indicates different change over time between treatment groups. If the interaction between time and treatment is not found to be significant, the interaction term will be omitted and an overall treatment effect will be tested.

D. QUALITY ASSURANCE

D1. Procedures in place to ensure the validity and integrity of the data

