Study Discontinuation

Criteria for removal from the study will include:

(1) substantial alcohol and other drug use that endangers the patient or requires a higher level of care such as inpatient or residential treatment; (2) psychiatric or medical deterioration that cannot be managed safely in the context outpatient treatment offered at the study clinics (e.g., acute suicide risk, acute medical problems); (3) Ongoing non-adherence with recommended clinical visits, absence from the clinic for more than 21 days; and (4) Pregnancy.

Patients who are exited from the trial for any reason will be offered a continued treatment in the community unless a higher level of care is indicated (inpatient or residential treatment), or the patient requests treatment elsewhere, in which care help with arranging referrals will be offered. Participants will be offer a weekly supply of buprenorphine for up to 30 days if they are being transitioned to another treatment program if they are removed from the trial. A clinic staff member, with physician backup, is available 24 hours per day by phone in case of emergency.

Participants may be removed from the trial if they repeatedly miss scheduled appointments or clinical worsening necessitates more intensive treatment (drop out criteria are defined above). Subjects who develop serious psychiatric symptomatology (e.g., psychosis, suicidal ideation, severe depressive symptoms) during the study period will be dropped from the study and appropriate clinical referrals will be made. A patient who's continued opioid use, places them at risk for self-destructive behavior or otherwise places them at significant risk will be discontinued from the study. This would include, but not be limited to, patients who become unconscious after using, engage in destructive or violent behavior while intoxicated, report driving while intoxicated, or develop medical complications from their opioid use. In all cases where subjects are discontinued from the study, the clinical research staff will assume clinical responsibility for the subjects until clinical referrals are operational.

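### SAP A2 and C3 analyse time to relapse alone, although the protocol and the SAP's own summary name relapse or dropout as the survival outcome

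*SAP*

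**What the plan says.** The SAP's opening study summary lists among the secondary outcomes "abstinence from other substances, time to relapse or dropout, and adverse effects". The protocol gives the same composite in its Lay Summary and in Specific Aims and Hypotheses.

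SAP A2 shortens this to "Time to relapse (survival outcome" and no longer mentions dropout. SAP C3, Secondary Analyses, carries the shorter form forward: "Time to relapse will be analyzed using survival analyses and Kaplan-Meier estimators". It gives no event rule, censoring rule, test or model for this outcome.

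The components of an event rule are already there. The protocol's End of Study Form (Assessment Instruments) records "the number of weeks of treatment completed from randomization to termination" and, as separate reasons for early termination, "documented relapse to opiates, resumption of buprenorphine maintenance, psychiatric worsening, medical worsening, or lost to follow--up". Dropout criteria are listed in the protocol's Criteria for Early Discontinuation ("Drop out criteria during the study period include" five items) and in SAP F3, Study Discontinuation, which includes "absence from the clinic for more than 21 days". Neither document says how these feed the survival outcome.

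**The concern.** The two descriptions are different endpoints. With the composite, a participant who leaves has an event. With relapse alone, a participant who leaves before a recorded relapse is normally censored, and Kaplan-Meier then assumes that this person's later relapse risk equals that of participants still under observation in the same arm.

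That assumption is doubtful here. The protocol's background describes withdrawal-like symptoms and rising craving when buprenorphine is stopped, and continues: "As a result, many will abandon the attempt at discontinuation and resume BUP maintenance". That sentence is about discontinuation in general and gives no rate for this trial. It does show that the sponsor expects exits driven by the same process that leads to relapse.

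At stake is the interpretation of one secondary result. From the same data, one analyst could follow the summary and count dropout, and another could follow C3 and censor it. The SAP summary says a signal that the naltrexone strategy is feasible and prevents relapse would encourage a larger trial, and this curve is one of several results that would be read for it.

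**Working it through.** 1. **The texts side by side.**

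| Place | Survival outcome |
|---|---|
| Protocol, Lay Summary | relapse or dropout |
| Protocol, Specific Aims and Hypotheses | relapse or dropout |
| SAP, opening summary | relapse or dropout |
| SAP A2, Secondary Outcomes | relapse |
| SAP C3, Secondary Analyses | relapse, Kaplan-Meier |

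The SAP is inconsistent with itself as well as with the protocol.

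2. **How each exit is treated if C3 is followed literally.**
- Documented relapse: event.
- Loss to follow-up: no relapse date exists, so it is censored. This follows from the method; no text states it.
- Buprenorphine resumption: open. The End of Study Form separates it from relapse, which points to censoring. The SAP's opioid urine panel includes buprenorphine, which points to counting it as use.
- Removal for another reason, such as pregnancy: censored.

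3. **The plan's own figure.** No event count or power is stated for the survival outcome. The only rates are in SAP A4, for the primary outcome: 25 per arm, 40% success (taper) against 77% (XR-NTX), 80% power at two-sided 5%. Unpooled check: 0.37 / sqrt((0.40 × 0.60 + 0.77 × 0.23)/25) − 1.96 = 0.904, or 81.7% power; the pooled formula gives 77.3%. The stated figure is reproduced closely enough to borrow the rates, but it does not bear on this point.

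4. **Illustration that the endpoints can differ.** Assumptions: week-25 failures (60% taper, 23% XR-NTX) stand in for composite events; hazards are constant; a share s of failures in each arm is relapse and the rest are other exits. The shares are invented.
- Total cumulative hazard H = −ln(success): taper −ln 0.40 = 0.916; XR-NTX −ln 0.77 = 0.261.
- Relapsed by Kaplan-Meier with other exits censored: 1 − exp(−sH).
- Cumulative incidence of relapse: s × failure proportion.
- Hazard ratio: (s_X × 0.261)/(s_T × 0.916).
- Expected events: 25 × (0.60 s_T + 0.23 s_X).

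| Relapse share, taper / XR-NTX | Events | 1 − Kaplan-Meier | Cumulative incidence | HR |
|---|---|---|---|---|
| 100% / 100% (composite) | 20.8 | 60% / 23% | 60% / 23% | 0.29 |
| 75% / 75% | 15.6 | 50% / 18% | 45% / 17% | 0.29 |
| 50% / 50% | 10.4 | 37% / 12% | 30% / 12% | 0.29 |
| 25% / 25% | 5.2 | 20% / 6% | 15% / 6% | 0.29 |
| 25% / 75% | 8.1 | 20% / 18% | 15% / 17% | 0.86 |
| 75% / 25% | 12.7 | 50% / 6% | 45% / 6% | 0.10 |

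With equal shares the hazard ratio is unchanged but rests on fewer events; approximate power (Schoenfeld) goes from 82% to 70%, 52% and 30%. With unequal shares the hazard ratio moves in either direction.

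5. **What the table does not show.** Exits here are independent of relapse risk by construction, so the censoring is non-informative. The values 0.86 and 0.10 are true relapse hazard ratios under those assumptions, and 1 − Kaplan-Meier and cumulative incidence are different estimands. None of this estimates informative-censoring bias. A participant abstinent at week 25 may also have relapsed earlier, which the illustration ignores.

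**The case against.** The best reply is that the harm is inferred. No text says that anyone is censored, the SAP's own summary still carries the composite, and A2 may simply be shorthand. That is fair as to intent. It does not settle which endpoint is run, because C3 is the analysis text and names relapse alone.

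A reader might infer that the SAP censors buprenorphine resumption. The documents do not support saying so: buprenorphine is in the opioid urine panel, and participants who relapse are themselves put back on buprenorphine (Protocol, Criteria for Early Discontinuation; SAP F3), so some resumptions would follow a relapse already counted.

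A reader might also infer that the psychiatrist's open-label choice of exit reason decides who has an event. No text makes the End of Study Form the source of the survival event. The protocol names Timeline Follow-Back confirmed by urine toxicology as the primary measure of substance use.

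Finally, this is one secondary outcome in an exploratory trial whose stated purpose (SAP A4) is a confidence interval for the odds ratio of treatment success. Week-25 abstinence, continuing abstinence at 12 and 25 weeks and the weekly use measure also bear on whether relapse is prevented. This limits the importance of the point; the conflict between the two endpoints stands.

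**Conclusion.** The conflict is established by the text: the composite appears in three places, and relapse alone in the two places that govern the analysis. Censoring of loss to follow-up follows from a literal reading of C3; censoring of buprenorphine resumption is possible but not established. Because these exits are plausibly related to relapse, the relapse-only curve could be biased.

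It is tempting to read the hazard ratios above as the size of that bias, or to say that it favours one arm. Neither is supported: the documents give no rates of relapse, resumption or dropout, and the illustration contains no informative censoring. It shows only that the two endpoints can give different answers. The primary analysis is unaffected. The point merits correction before data are seen because the correction is simple and removes a choice that could change the survival result.

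**What to change.** In SAP A2 and C3, restore the protocol's composite as the survival event. Time it from randomization to the first of (a) relapse, (b) buprenorphine taken outside the assigned regimen's schedule, or (c) dropout, with administrative censoring at week 25. Apply (b) identically in both arms; scheduled taper doses are not events.

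Report relapse alone as a supporting cumulative-incidence analysis with resumption and dropout as competing events. Tabulate exits by End of Study Form reason and arm.

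Before data are seen, the sponsor should set:
- the relapse threshold, including how a missing sample is treated, preferably in calendar weeks because visits range from daily at induction to twice monthly in months 4–6 (Protocol, Study Procedures);
- whether removals clearly unrelated to opioid use, such as pregnancy, count as dropout. The protocol's word alone does not decide this.

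The drawback is that the composite mixes relapse with other exits, which the supporting analysis and the table address. The cost is SAP wording, one added analysis and one table. Timeline Follow-Back, urine results and exit reasons are already collected, so no visits, participants or staff are added.

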The primary purpose of this proposed R21 is to estimate the 95% confidence interval (CI) for the treatment effect size, in this case the odds ratios of treatment success. The resulting 95% CIs provide considerably more information than hypothesis tests; it provides a range of plausible parameter estimates. Such range of effect sizes (especially the estimates from the lower end of the 95% CIs) can be used to conservatively estimate potential effect size in larger clinical trials. The following power calculations are only in support of this study proposal and for the purpose of sample size calculation. We assume that the observed proportion of successful BUP discontinuation in the buprenorphine taper group ranges from 30-50% (we assume higher success rate than in the previous buprenorphine taper studies due to longer period of stabilization). With 25 subjects in each arm, we have 80% power to detect a significant treatment success difference of 37% (e.g. 40% of treatment success in BUP compared to 77% treatment success in XR-NTX arm) on 5% level of significance. This is a robust effect that would be clinically meaningful.

The primary aim of this pilot study is to evaluate feasibility, tolerability, acceptability, and safety of two methods of discontinuing treatment with buprenorphine. The proposed sample size of 60 enrolled and 50 individuals randomized to two treatment arms can provide useful information for subsequent confirmatory clinical trial. We have chosen this sample size to minimize the cost and also to reach the study end within two years. 50 randomized subjects will provide large enough sample size to estimate the potential effect size in 95% confidence interval with reasonable precision.

B. TRIAL MANAGEMENT

B1. Data Collection Centers

All data will be collected at one site: New York State Psychiatric Institute's Outpatient Substance Abuse Research Service (STARS)-downtown at [name]. In our center, we have adopted StudyTrax, a comprehensive electronic system for clinical trials, which we will use to collect and manage data. As many entry forms and study calendars are already programmed, starting of a study can be expedited. Data will be analyzed using SPSS-PC, SAS, and HLM.

B2. Projected Time Table

Based on the recent rate of recruitment in our center and the planned sample size the study is estimated to take 24 months to complete.

B3. Target Population Distribution

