The most common side effect associated with injectable naltrexone is injection site reaction. XR-naltrexone is administered as a gluteal intramuscular injection and injection site reactions, mostly pain, and occurs in approximately 5% of patients in opioid treatment studies. These reactions are generally mild and include pain, tenderness, indurations, bruising, pruritus and swelling. Generally these reactions last 1--3 days. Rare skin reactions at the site of the injection have been reported, including sterile abscesses, which may relate to inadvertent injection into fatty tissue, rather than muscle. Patients will be informed of this risk, and baseline physical evaluation will include examination of the buttock for excessive adiposity. If a patient is examined by a physician and found to have an abscess, necrosis, cellulitis or extensive swelling, an appropriate surgical referral will be made.

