The implications of random assignment to treatment conditions will be discussed with patients. One of the treatments could be more or less effective for a given patient. The alternative choices of continuing buprenorphine maintenance outside of the study or injection naltrexone, detoxification and counseling without medication (so called “drug-free” treatment), will be discussed with patients, as well as options of pursuing such treatments at other treatment programs available to the patients in the New York area. These will be discussed with patients at the time of consent, and revisited if relapse occurs. Patients will also be informed, and reminded that the study is voluntary and that they can opt for any of these options at any point during the study.

Assessments

The structured interviews, rating scales, and questionnaires should add no physical risk. However, because many of the interviews and assessments are time-consuming to complete and involve topics of a sensitive nature, some people have found them to be physically or emotionally tiring. Patients are informed prior to study entry that they can refuse to answer any questions and that they can request to stop at any time. If a participant becomes agitated during any of the interviews or assessments, he or she will be provided with therapeutic assistance.

Other Risks

Blood draws may cause slight discomfort at the site of needle entry, can result in infection at the site if hygienic/sterile techniques aren't used, or can result in a small bruise.

Participants will receive cash card compensation and incentives during the study that could pose a risk of providing more available funds to purchase illicit opioids. However, the form of compensation- a cash card limits this risk.

Potential Benefits of the Proposed Research

Participants will receive up to 25 weeks of free treatment.

F2. Collection and Reporting of Adverse Events (AEs) and Serious Adverse Events (SAEs)

Definitions

An **adverse event** is any unwanted experience or event occurring during the course of a clinical trial. An adverse event is defined as **unexpected** whenever the nature and severity of the event is not consistent with the known product information.

Relationship to Study Drug

The investigator will document his/her opinion of the relationship of the event to the study drug as follows:

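### Adverse events go to the covariate-adjusted logistic model with no sparse-data fallback, outcome unit or start date stated; counts by arm with risk differences would serve better

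*SAP*

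**What the plan says.** SAP A2 gives the last secondary outcome as "5) Adverse events (SAFTEE) (dichotomous"). Unlike outcomes 1 and 4 it is not marked longitudinal. No event type, counting unit or time window is attached.

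SAP C3, Secondary Analyses, then states: "Dichotomous outcomes will be analyzed similarly to primary hypothesis with logistic regressions". The primary analysis is a "logistic regression adjusted for specified covariates (primary opioid type, length of BUP maintenance, and average dose"), and the general paragraph of C3 repeats that "The analysis will be adjusted by three preselected covariates". C3 names no exact or penalised method, no tabulation of events by arm and no rule for an arm without events.

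On the events themselves, SAP F1 says: "The most common side effect associated with injectable naltrexone is injection site reaction". It puts the frequency at about 5% in opioid treatment studies. SAP F2 defines an adverse event as one that "is any unwanted experience or event occurring during the course of a clinical trial". SAP Table 1 schedules SAFTEE in a weekly column that combines buprenorphine stabilisation with the taper, and the 4-week stabilisation precedes randomisation. The Protocol (Assessment Instruments, SAFTEE) and SAP E1 both have onset and severity recorded.

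**The concern.** With about 25 patients per arm, many individual adverse events will occur a handful of times or not at all. Maximum-likelihood logistic regression has no finite treatment odds ratio when one arm has no events or only events, and adding three covariates creates further ways for the fit to separate. SAP A4 says that the pilot exists chiefly to produce interval estimates, and it counts tolerability and safety within the primary aim. For a sparse event, the stated method may give no usable interval.

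Two gaps in the definition add to this. The unit of the outcome (any event, or each event type) decides which failure is possible. The absence of a start at randomisation leaves open whether a patient with an event only in the lead-in, when both future arms are treated alike, is scored as having the outcome.

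**Working it through.** **Sample size.** SAP A4: "With 25 subjects in each arm, we have 80% power to detect a significant treatment success difference of 37" percentage points, illustrated as "40% of treatment success in BUP compared to 77% treatment success in XR-NTX arm", at the 5% level (two-sided in C3). With unpooled variance the standard error is √[(0.40×0.60 + 0.77×0.23)/25] = 0.129, and 0.37/0.129 − 1.96 gives 81.7% power. With pooled variance, power is 77.3%. The stated 80% lies between the two and is not in dispute. It is used here only to fix 25 per arm.

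**Reading A: one model per event type.**

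*Injection site reaction, at the SAP's 5%.*
- Expected cases in the XR-NTX arm: 25 × 0.05 = 1.25. Under the taper regimen as the SAP describes it there are no injections, so none.
- P(no case at all) = 0.95^25 = 0.277, and then nothing can be fitted. Otherwise every case is in one arm and the maximum-likelihood odds ratio is infinite.
- Illustration with assumed counts of 5/25 v 0/25 and treatment alone in the model: coefficient 22.2, standard error about 15,892. That is a fit running off to infinity.

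*Events possible in both arms (rates assumed; the documents give none by arm).* P(at least one arm has 0 of 25) = 1 − [1 − (1 − a)^25][1 − (1 − b)^25].

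| Rates in the two arms | An arm with 0 events (formula) | Separation in adjusted model (simulated) |
|---|---|---|
| 2% v 2% | 84% | 91% |
| 5% v 5% | 48% | 63% |
| 5% v 10% | 33% | 44% |
| 10% v 10% | 14% | 22% |
| 20% v 20% | 0.8% | 2% |

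For 5% v 5%: 1 − (1 − 0.277)² = 0.478. The last column comes from 2,500 simulated trials per row, with treatment, a binary opioid type, a continuous treatment length and a dose of 2, 4, 6 or 8 mg. The covariate distributions are assumptions. The column counts separation anywhere in the model, which need not always involve the treatment term.

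**Reading B: one any-event indicator per patient.**
- The one-arm problem goes, but a ceiling can replace it. By symmetry with the formula above, an arm with 25 of 25 occurs in 14% of trials at a 90% rate in both arms and in 48% at 95%. The simulated adjusted model separates in 23% and 61%. Such rates are assumptions, but not remote ones: an independent 10% chance per week over 25 weeks gives 1 − 0.90^25 = 93%.
- Lead-in: if 10% to 20% of patients report an event in a given week (assumed, weeks independent), the share already positive before randomisation is 1 − 0.90^4 = 34% to 1 − 0.80^4 = 59%. If that share L is equal in both arms and unrelated to later events, the observed difference is (1 − L) times the true one, that is 66% down to 41% of it. Clustering of events within patients would reduce L.

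The zero-event figures belong to reading A and the ceiling and lead-in figures to reading B. They are not to be added together.

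**What a simpler summary returns.** For 5/25 v 0/25: 20% (exact 95% CI 6.8% to 40.7%) against 0% (0% to 13.7%), Fisher p = 0.050. For 1/25: 4% (0.1% to 20.4%). Intervals exist in every case.

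**The case against.** A reader might infer that the planned model can never give an estimate for adverse events. The documents do not support that. It holds only for analysis by event type with ordinary maximum likelihood, and the SAP neither states nor excludes either. Firth's penalised logistic regression is still logistic regression, and it gives an odds ratio of 13.7 (95% CI 0.67 to 278) for 5/25 v 0/25 and 3.1 (0.11 to 86) for 1/25 v 0/25. The fair criticism is that no such option is named. Intervals that wide also favour reporting risks directly.

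Injection site reactions need a rate rather than an arm comparison whatever the model, and SAP F1 describes them as generally mild and brief. The serious risks it discusses, relapse and overdose after stopping, can occur in both arms. That stands, and it limits the weight of the injection-site example.

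A reader might also infer that lead-in events will be counted. No instruction says so. The F2 wording is a reporting definition, the instrument's name refers to treatment-emergent effects, and recorded onset dates allow a later cut. But patients are already on buprenorphine from the research clinic in the lead-in, so the name alone does not set the start at randomisation.

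Nor are safety data lost: events are listed individually (SAP E1) and go to the DSMB and NIDA (SAP H3). Those are monitoring outputs, not a comparison of arms. Finally, A4 also calls the odds ratio of treatment success the primary purpose, and neither aim in C3 concerns safety, so importance should not be overstated.

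One dependency needs reconciling. The Protocol's Regimen 2 paragraph carries a sentence on further XR-NTX injections, which the SAP places under Regimen 1. Both documents also allow transfer to naltrexone after a failed discontinuation. Confinement to one arm therefore means under the assigned regimen as the SAP describes it.

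**Conclusion.** The concern holds in a conditional form, as a cheap improvement rather than a threat to the trial's main result. The only between-arm adverse-event analysis in the plan is the three-covariate logistic model, with no sparse-data fallback and no stated outcome unit or start. By event type, with maximum likelihood, there is no finite odds ratio for an event confined to the XR-NTX regimen. An arm without events arises in about 48% of trials at 5% in both arms, 14% at 10% and under 1% at 20%. So failure is common only at about 5% or below, and rare from 20%. For a single any-event indicator the risks are a ceiling and, if lead-in events are counted, dilution.

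The size rests on 25 per arm and on assumed event rates; the 5% for injection site reactions is the only rate taken from the documents. The missing start date is the lesser part, because the data to set it are already collected.

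**What to change.** In SAP C3, take adverse events out of the sentence on dichotomous outcomes and state:

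- Adverse events are summarised by randomised arm as n/N, both for any event and by event type.
- Arms are compared by a risk difference with a score (Miettinen-Nurminen) or exact 95% CI, and Fisher's exact p where wanted.
- For injection site reactions, only the XR-NTX arm rate is given, with an exact CI and no arm comparison.
- Only events with onset or worsening after randomisation count, using the recorded onset and severity. Lead-in events are listed separately.

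Separately, reconcile the placement of the further-injection sentence between the Protocol's Regimen 2 paragraph and the SAP.

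Cost: SAP wording only, a simpler analysis and no new data. The adverse-event comparison loses covariate adjustment, which sparse counts could hardly support: at 10% in both arms, 50 × 0.10 = 5 expected events would inform four slope coefficients. No method makes 1/25 v 0/25 informative, but this one reports it honestly.
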